4.2.2 Secondary and Exploratory Outcome Variables

1) Composite executive function test scores (Secondary)

Time frame: This measure will be collected at baseline (T0), immediately after 6 weeks of intervention (T1), and 12 weeks thereafter (T2) from all subjects.

Rationale: We will calculate the composite z-scores of the executive function test scores (i.e., Stroop, F-A-S letter fluency, and Trail Making A-B tests) for all subjects.

Change in composite executive function test scores from T0 to T1 and across T2 will be the secondary cognitive outcomes of the study. Significant increase in these scores at T1 will be considered improved executive function. Significant increase in these scores across T2 will be considered sustained improvement in executive function.

2) Local and global functional connectivity-based graph measures (Secondary)

Time frame: This measure will be collected at baseline (T0), immediately after 6 weeks of intervention (T1), and 12 weeks thereafter (T2) from all subjects.

Rationale: We will calculate the local (i.e., clustering coefficient) and global (i.e., betweenness centrality) network graph measures during mental imagery and video-watching tasks in the MRI scanner. These measures will provide information about the context-dependent changes in the functional organization of the brain networks.

Change in graph measures from T0 to T1 and change in graph measures across T2 will be secondary imaging outcomes the study. Significantly increased task-specific clustering coefficient in major networks (e.g., default mode network during mental imagery and frontoparietal executive network during video-watching) and significantly increased context-dependent betweenness centrality between major network nodes (e.g., stronger between the default mode and frontoparietal networks during mental imagery) at T1 will be considered improved task-specific functional differentiation of these networks. Significant increases in the same graph measures across T2 will be considered sustained improvement in task-specific functional differentiation of these networks.

3) Modified Six-Elements Test scores (Exploratory)

Time frame: This measure will be collected at baseline (T0), immediately after 6 weeks of intervention (T1), and 12 weeks thereafter (T2) from all subjects.

Rationale: The Modified Six-Elements Test is a measure of goal-directed planning and execution.

Change in these test scores from T0 to T1 and across T2 will be the secondary cognitive outcomes of the study. Significant increase in these scores at T1 will be considered improved performance in goal-directed planning and execution. Significant increase in these scores across T2 will be considered sustained improvement of performance in goal-directed planning and execution.

4) Global cognition scores (Exploratory)

Time frame: This measure will be collected at baseline (T0), immediately after 6 weeks of intervention (T1), and 12 weeks thereafter (T2) from all subjects.

Rationale: The Repeated Battery for the Assessment of Neuropsychological Status (RBANS) is a commonly used battery with alternate versions allowing repeated testing of the cognitive domains of attention, verbal and visual memory, language, and visuospatial functioning.

Change in total RBANS scores from T0 to T1 and across T2 will be the exploratory cognitive outcomes of the study. Significant increase in these scores at T1 will be considered improved global cognition. Significant increase in these scores across T2 will be considered sustained improvement of global cognition.

5) Post-training brain-cognition relationship (Exploratory)

Time frame: This measure will be collected at baseline (T0), immediately after 6 weeks of intervention (T1), and 12 weeks thereafter (T2) from all subjects.

Rationale: We will examine whether the post-training changes in whole-brain pairwise functional connectivity and graph measures will predict the post-training differences in the cognitive function in each group at T1 and T2.

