Change in composite executive function test scores from T0 to T1 and across T2 will be the secondary cognitive outcomes of the study. Significant increase in these scores at T1 will be considered improved executive function. Significant increase in these scores across T2 will be considered sustained improvement in executive function.

2) Local and global functional connectivity-based graph measures (Secondary)

Time frame: This measure will be collected at baseline (T0), immediately after 6 weeks of intervention (T1), and 12 weeks thereafter (T2) from all subjects.

Rationale: We will calculate the local (i.e., clustering coefficient) and global (i.e., betweenness centrality) network graph measures during mental imagery and video-watching tasks in the MRI scanner. These measures will provide information about the context-dependent changes in the functional organization of the brain networks.

Change in graph measures from T0 to T1 and change in graph measures across T2 will be secondary imaging outcomes the study. Significantly increased task-specific clustering coefficient in major networks (e.g., default mode network during mental imagery and frontoparietal executive network during video-watching) and significantly increased context-dependent betweenness centrality between major network nodes (e.g., stronger between the default mode and frontoparietal networks during mental imagery) at T1 will be considered improved task-specific functional differentiation of these networks.

Significant increases in the same graph measures across T2 will be considered sustained improvement in task-specific functional differentiation of these networks.

3) Modified Six-Elements Test scores (Exploratory)

Time frame: This measure will be collected at baseline (T0), immediately after 6 weeks of intervention (T1), and 12 weeks thereafter (T2) from all subjects.

Rationale: The Modified Six-Elements Test is a measure of goal-directed planning and execution.

Change in these test scores from T0 to T1 and across T2 will be the secondary cognitive outcomes of the study. Significant increase in these scores at T1 will be considered improved performance in goal-directed planning and execution. Significant increase in these scores across T2 will be considered sustained improvement of performance in goal-directed planning and execution.

4) Global cognition scores (Exploratory)

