Based on the pairwise functional connectivity maps, we will compute the clustering coefficient and betweenness centrality representing local and global graph measures, respectively, using the CONN Toolbox.⁵³ These graph measures associated with the mental imagery and video-watching tasks performed at baseline (Visit 2) and immediately upon conclusion of the 6-week intervention (Visit 3) will be compared between the PD-MI and PD-Con groups using a 2x2 mixed ANOVA with an interaction term (dependent variables: graph measures, between-subject factor: group, within-subject factor: time with two levels, i.e., baseline and post-training, interaction: group-by-time). We will use the FDR-correction for multiple comparisons ($p < 0.05$, two-tailed).¹⁰²

Behavioral scanning data: We will add up the number of key elements of the recorded mental imagery descriptions for each scan (e.g., entities, sensory descriptions, spatial/temporal references, thoughts, actions, emotions, task components) and average them across scans to obtain an average imagery content score per subject. We will also average the number of correct answers to content-related questions after video-watching scans to obtain an average accuracy score per subject. The average mental imagery content and video-watching accuracy scores performed at baseline (Visit 2) and immediately upon conclusion of the 6-week intervention (Visit 3) will be compared between the two groups using a 2x2 mixed ANOVA with an interaction term (dependent variables: average scores, between-subject factor: group, within-subject factor: time with two levels, i.e., baseline and post-training, interaction: group-by-time) ($p < 0.05$, two-tailed).

AIM 3: To determine whether the cognitive and brain effects of mental imagery training in PD are sustained

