To compare the task-specific whole-brain functional connectivity changes between the groups, we will perform pairwise functional connectivity analyses using the generalized psychophysiological interaction (gPPI) model. We will first convolve the 3-min task blocks in each mental imagery and video-watching run with the canonical hemodynamic response function. We will use the functionally defined cortical and subcortical nodes (N=268) of the whole-brain Shen atlas.⁵² For each subject, we will extract the average blood oxygenation level-dependent signal time courses calculated via the gPPI model from these nodes and correlate them with each other using Pearson correlations. The r values will correspond to the functional connectivity strength between node pairs. We will Fisher z-transform the r values and obtain group-level functional connectivity maps for statistical analyses.

Graph analysis

To compare the task-specific changes in local and global network properties between the groups, we will perform graph analyses on the pairwise functional connectivity data. Specifically, we will compute the 1) clustering coefficient, which shows the connectivity strength between neighboring nodes and is a measure of local network efficiency, and 2) betweenness centrality, which shows how well-connected a particular node is with all other nodes and is a measure of that node's potential as an integrative hub.¹⁰⁶ These graph measures will then be used in statistical analyses.

Sex as a biological variable

Sex differences in normal cognitive aging have been reported.¹⁰⁷ Reports on sex differences in PD-related cognitive decline have been variable. Sex differences in cognition in de novo PD patients have been found to be similar to those in normal aging.¹⁰⁸ On the other hand, male sex was found to be associated with PD-MCI,¹⁰⁹ and poorer performance in male vs female PD patients in executive functioning and processing speed have been demonstrated.¹¹⁰ In our study, both groups will be sex-matched and we will use sex as a covariate in separate analytical models to examine the potential sex-related differences in training response.

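### Increased betweenness centrality cannot be read as improved differentiation of the default mode and frontoparietal networks, because it is a single-node hub measure with no value for a pair of networks

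*Combined protocol and SAP*

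**What the plan says.** Section 4.2.2, item 2, repeated in the synopsis, makes the clustering coefficient and betweenness centrality the secondary imaging outcomes at T1 and T2. The betweenness part of the success rule is "significantly increased context-dependent betweenness centrality between major network nodes (e.g., stronger between the default mode and frontoparietal networks during mental imagery". Together with increased clustering within networks, this "will be considered improved task-specific functional differentiation of these networks". The hypothesis in section 3.1 is also worded as improved differentiation of core networks.

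Section 5.4.3 (Graph analysis) describes the measure as "betweenness centrality, which shows how well-connected a particular node is with all other nodes", and adds that it gauges that node's potential as an integrating hub. On construction it says only that "we will perform graph analyses on the pairwise functional connectivity data". The nodes come from the atlas: "We will use the functionally defined cortical and subcortical nodes (N=268) of the whole-brain Shen atlas".

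Section 5.4.1, Aim 2, states that "we will compute the clustering coefficient and betweenness centrality representing local and global graph measures, respectively, using the CONN Toolbox". The graph measures then enter a 2x2 group-by-time mixed ANOVA, FDR-corrected and two-tailed. Aim 3 extends this to three time points, and Aim 4 uses the graph measures as predictors of cognitive change.

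No section says which nodes represent each network, how node values are combined, or what threshold or weighting turns the connectivity matrix into a graph.

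**The concern.** Two things do not fit together.

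- **Unit of measurement.** The rule looks for betweenness lying between two networks, but the computed quantity belongs to one node relative to all others. Some unstated step must turn node values into a statement about a network pair. If that step is left open, nodes and aggregation could be chosen after the results are known.
- **Meaning.** By the plan's own description, betweenness marks integration. The rule credits its increase as differentiation, and its example is a stronger link between two networks. An integration finding would thus be counted in support of the differentiation hypothesis in 3.1.

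At stake is the secondary imaging conclusion at T1 and T2, and the reading of any Aim 4 association that uses betweenness. A significant increase could be reported as improved differentiation when it shows neither that nor closer coupling.

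**Working it through.** The plan gives no figure to reproduce on this point, so the check has three parts.

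**1. What the analysis produces.** With 268 nodes, each scan and task yields 268 betweenness values, one per node. The connectivity matrix holds 268 x 267 / 2 = 35,778 node-pair values. Only the matrix contains quantities that lie between two networks.

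**2. What is guaranteed about direction.** In a connected binary graph with n nodes, betweenness summed over nodes equals the sum over node pairs of (shortest path length - 1). With the usual normalisation, mean betweenness = (L - 1)/(n - 2), where L is mean path length. Adding links to a connected graph cannot lengthen L, so the whole-graph mean cannot rise. Nothing similar holds for a chosen node or network.

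Two simulated 20-node modules (link probability 0.5 within a module, 30 replicates) illustrate this:

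| Cross-links, placed at random | 0 | 1 | 4 | 16 | 64 | 200 |
|---|---|---|---|---|---|---|
| Whole-graph mean betweenness | 0.006 | 0.045 | 0.034 | 0.025 | 0.018 | 0.013 |

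The first link raises the mean, because it connects the modules; later links lower it. As a check on the formula, 0.0338 at 4 links gives L = 1 + 38 x 0.0338 = 2.28, and 0.0181 at 64 links gives L = 1.69.

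Now let one node gain links to the other module when 16 cross-links already exist:

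| Links gained by that node | 0 | 1 | 5 | 10 | 20 |
|---|---|---|---|---|---|
| Its betweenness | 0.008 | 0.030 | 0.085 | 0.142 | 0.245 |
| Whole-graph mean | 0.0254 | 0.0248 | 0.0241 | 0.0233 | 0.0216 |

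The same added linkage moves the node up and the average down.

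**3. A model of the planned size.** The model has 268 nodes in eight networks, with the correlation between default mode and frontoparietal signals raised from -0.10 to 0.75. Network sizes (20 and 30), loadings, thresholds and 500 time points are assumptions, because the plan gives no graph settings. There are four replicates per setting. Entries are mean betweenness over the nodes of both networks, x1000:

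| Threshold | -0.10 | 0.30 | 0.75 | First to last |
|---|---|---|---|---|
| Densest 5% of links | 0.108 | 0.103 | 0.424 | x3.9 |
| Densest 15% | 4.392 | 5.207 | 5.523 | +26% |
| Densest 30% | 2.239 | 2.964 | 2.823 | +26% |
| r > 0.15 | 4.906 | 5.348 | 4.931 | +0.5% |
| r > 0.25 | 0.176 | 0.804 | 0.111 | -37% |

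From 0.30 to 0.75 the sign also differs: up 6% at the 15% density (5.523/5.207), down 5% at 30% (2.823/2.964), and down 86% at r > 0.25 (0.111/0.804). The two networks can move apart as well. At the 15% density, raising the correlation from 0.45 to 0.75 took the default mode mean from 5.245 to 6.540 and the frontoparietal mean from 5.541 to 4.845. Threshold, node set and aggregation each affect the answer.

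**The case against.** The strongest defence is that the analysis itself is workable. Aim 2 specifies an FDR-corrected, two-tailed mixed ANOVA that can be run node by node, and the rule's phrase can be read loosely as the betweenness of nodes within the named networks. This stands: the test can be run. What it cannot do is deliver the stated conclusion. A two-tailed test detects change either way, but the rule attaches benefit only to an increase, and calls it differentiation.

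A second defence is that the label covers clustering and betweenness jointly, and that task-specific differentiation could mean reconfiguration according to context. That reading is possible, so the clash of terms is not a proven contradiction. The plan does not give this definition, however, and describing betweenness as a hub-integration measure pulls the other way.

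Third, coupling between node pairs is already the primary imaging outcome. That is true, and it makes the fix easy, but it does not repair the secondary rule.

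A reader might go further and infer that betweenness falls as two networks become more linked, so that the rule points the wrong way and the trial would record the wrong sign. The documents do not support this. The fall is assured only for the whole-graph mean when links are added to an already connected graph. A node gaining cross-network links rose, and at fixed density the two networks' betweenness rose overall. A reader might also infer that the plan equates betweenness with coupling. Its stated label is differentiation; coupling is suggested only by the bracketed example.

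**Conclusion.** The concern holds for the success rule and its interpretation. By the plan's own definition no betweenness value exists for a pair of networks, and an increase does not establish differentiation or stronger between-network coupling. This rests on comparing 4.2.2 and the synopsis with 5.4.3 and needs no simulation.

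The simulations add only that the sign under stronger linkage is undetermined: from -37% to about 3.9 times the starting value across five plausible thresholds. Those figures depend on assumed network sizes, loadings and thresholds and do not predict the trial's result.

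The matter is worth correcting before analysis but is limited in reach. It touches one of two secondary graph measures and its use in Aims 3 and 4. The clustering coefficient, the primary imaging outcome and the sample size are not affected.

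**What to change.** In 4.2.2 and the synopsis, remove the rule that increased betweenness means improved differentiation. Replace it with two quantities per subject, visit and task, taken from the Fisher-z matrices already planned:

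- **Integration, I:** mean z over all node pairs with one node in the default mode and one in the frontoparietal network.
- **Differentiation, D = W - I:** W is mean z over pairs within the same network.

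Name the atlas nodes assigned to each network, and state the expected direction of I and D separately for imagery and video-watching. With W unchanged, a rise in I lowers D by the same amount, so the plan must say which is expected in which task. Both can enter the existing mixed ANOVA.

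If betweenness is kept, report it descriptively as hub centrality of pre-named nodes, at a stated threshold and weighting, with no benefit claim.

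The cost is protocol wording and a few lines of post-processing, with no new data. The small downside is that betweenness no longer supports a statement of success.

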4.3 Study Population

The study population will be subjects with PD defined according to the Movement Disorders Society (MDS) diagnostic criteria with mild-to-moderate PD⁷⁵, who do not have mild cognitive impairment⁷⁶, aged 40 and above, and are physically independent.

Idiopathic PD is an adult-onset neurological disorder. In the United States, the incidence of idiopathic PD cases before the age of 40 is extremely low.⁷⁷ Therefore, individuals with PD who are 40 years and older will be included, and there will be no upper age limit for participation in the study.

There is no restriction for gender, race, or ethnicity. Parkinson's disease affects more males than females with most studies reporting a male-to-female ratio ranging from 1.3 to 2.⁷⁸ We will aim to reflect a male-to-female ratio of 1.5 in subject selection.

There is no restriction in participation regarding race or ethnicity. We will seek a racially and ethnically diverse enrollment. According to the United States Census Bureau, the 2020 census demographic data in Connecticut showed the following distribution:⁷⁹ White only 66.4%, Black only 10.8%, Asian only 4.8%, Hispanic or Latino 17.3%. The percentage of other racial categories was very small. The numbers in the planned enrollment table were calculated based on these ratios.

Subjects will be recruited through:

1. The Yale Movement Disorders outpatient clinics
2. The outpatient clinics in the new Yale PD Comprehensive Care Center
3. The local PD support groups and nonprofit organizations (e.g., American PD Association Connecticut Chapter, Beat PD Today exercise program) that provide educational and wellness programs for the greater PD community in Connecticut
4. Neurology practices in Connecticut who care for patients with PD.
5. JDAT recruitment services (EPIC/MyChart alerts & mailing)
6. Department/Center newsletters
7. The YCCI recruitment database
8. Recruitment letters

Table 2. Planned Enrollment

	Not Hispanic or Latino		Hispanic or Latino		Total
	F	M	F	M	
American Indian/Alaska Native	0	0	0	0	0
Asian	2	3	0	0	5
Native Hawaiian or other Pacific Islander	0	0	0	0	0

Black or African American	5	8	1	1	15
White	32	47	9	12	100
More than one race	0	0	0	0	0

4.3.1 Number of Participants

We will enroll 120 individuals. Eligible subjects will be randomly assigned to either the PD-MI (N=60) or PD-Con (N=60) group.

4.3.2 Eligibility Criteria/Vulnerable Populations

In order to be eligible for inclusion in the study, an individual must meet all of the following criteria:

- Subjects with a diagnosis of idiopathic PD defined according to the International Parkinson and Movement Disorder Society (MDS) Clinical Diagnostic Criteria for PD⁷⁵
- Age \geq 40 years
- Expected to be on a stable dopaminergic medication regimen throughout the study period

Any individual who meets any of the following criteria will be excluded from participation in this study:

- Age < 40 years
- Non-English speaking
- Pregnancy
- Breastfeeding
- Excessive alcohol consumption (> 7 drinks per week for women, > 14 drinks per week for men) or illicit substance use
- History of a neurological disorder such as a brain tumor, stroke, central nervous system infection, multiple sclerosis, movement disorder (other than PD), or seizures
- History of schizophrenia, bipolar disorder, attention deficit disorder, or obsessive-compulsive disorder
- History of head injury with loss of consciousness longer than a few minutes
- Metallic surgical implants or traumatically implanted metallic foreign bodies
- Inability to lie flat for about an hour in the MRI scanner
- Discomfort being in small, enclosed spaces
- Dementia at screening (Video-Montreal Cognitive Assessment score < 21/30⁸⁰⁻⁸²)
- Cognitive problems in activities of daily living suggestive of more than mild cognitive impairment (PD Cognitive Functional Rating Scale > 4⁸³)
- Mild cognitive impairment according to the MDS Level II comprehensive assessment criteria (> 2 SD below the norm in two tests in a single cognitive domain or in one test in two separate cognitive domains). Note: The cutoff of 2 SD below the norm will apply to all domains including attention, verbal and visual memory, language, visuospatial skills, and executive functions.⁷⁶
- Hoehn & Yahr stage > 3 (i.e., able to stand and walk, but not fully independent⁸⁴)
- Focal neurological findings on exam that suggest cerebral pathology other than that associated with parkinsonism
- Motor symptoms that could potentially introduce too much motion artifact in the imaging data (e.g., MDS-Unified PD Rating Scale resting tremor score > 2 in limbs, head/chin tremor, or more than mild dyskinesia by history or exam⁸⁵)
- Failure to adhere to training and homework requirements (i.e., less than 75% adherence to one-on-one sessions and less than 50% homework completion rate)

- Failure to adhere to protocol

Vulnerable Populations:

Women of childbearing potential will not be included, if they are pregnant or breastfeeding. Women who are 50 years of age and older or who have absence of menses for two years will not receive pregnancy tests. All other women will receive urine pregnancy test in two weeks before the scheduled MRI session.

5 Study Methods/Procedures

